## 2. Asthma Exacerbation

In this study an asthma exacerbation will be defined according to the recommendation of the NIH Outcomes Workshop (84) as a worsening of asthma requiring the use of a systemic corticosteroid (at least 2 days of treatment) to prevent a serious outcome. In accordance with the Expert Panel recommendations, data will be captured on the following exacerbation-related outcomes:

- a. All worsening asthma events in which systemic corticosteroids were initiated to prevent a serious outcome, including use of systemic corticosteroids in association with any form of healthcare provider encounter
- b. All asthma-specific ED or urgent care visits that involved treatment with systemic corticosteroids
- c. All asthma-specific hospitalizations that involved treatment with systemic corticosteroids (also reported as an SAE)
- d. All asthma-specific intensive care unit admissions or intubations (also reported as an SAE)
- e. All deaths (all-cause and asthma-related; also reported as an SAE)

For the purpose of this study, 2 courses of systemic corticosteroids must be separated by at least 1 week to count as 2 exacerbations and to be documented as such.

3. Episode of problematic asthma

Any asthma-related unscheduled healthcare visit (outpatient, urgent care, ED).

4. Respiratory tract infection

Patient-reported episodes of upper respiratory tract infection (cold), sore throat, strep throat, bronchitis, pneumonia, ear infection, and acute sinusitis (sinus infection) will be documented from structured interviews occurring at each study visit and planned study phone call. This approach has been used successfully in large pediatric asthma trials. (80)

---

#### 8.1.2 LABORATORY EVALUATIONS

Specimens for evaluation include:

- Safety assessments (volumes to be determined by laboratory facility at local site; methodology to be determined by the laboratory facility at the local site)
  - Urine for pregnancy test for female participants of childbearing potential (done only at Visit 1, Visit 4, and Visit 6/Early Termination).
  - Blood for serum 25(OH)D level at Visit 1 (Screening) and Follow-up visit 9 (week 28).
  - Urine for creatinine/calcium ratio to be done at Screening and study Visits 3, 4, 5, and 6. Blood for serum calcium will be collected if indicated due to a high urine calcium/creatinine ratio.
- Study assessments (to be performed by a College of American Pathologists [CAP] accredited and Clinical Laboratory Improvement Amendments [CLIA] certified central laboratory).
  - 25(OH) vitamin D level by liquid chromatography/tandem mass spectrometry (specimen collection per laboratory manual) to be done at Baseline (visit 2) and study Visits 3, 4, 5, and 6 as well as follow-up (visits 7, 8, and 9). There is an optional visit, with a blood draw for vitamin D analysis, between Week 1 and 3, if the participant volunteers for this.
  - Cytokine panel (IL-2, IL-6, IL-10, IL-17, and TNF-alpha) by immunoassay as cytokine panel (specimen collection per laboratory manual) to be done at Baseline and at Visit 6 and, if the participant agrees to blood collection by venipuncture, at Visits 3, 4, and 5, and Follow-up (visits 7, 8, and 9).

- Leptin by electrochemiluminescence (specimen collection per laboratory manual) to be done at Baseline and at Visit 6 and, if the participant agrees to blood collection by venipuncture, at Visits 3, 4, and 5, and Follow-up (visits 7, 8, and 9).

### **Laboratory determinations of vitamin D levels**

25(OH)D levels for study endpoints will be determined at a CAP accredited and CLIA certified central laboratory. Vitamin D levels will be obtained at the local laboratory for determining inclusion criteria (25(OH)D level less than 30 ng/ml but great than 10 ng/mL) and for safety measurements at the local investigator's discretion, ensuring prompt turn around.

## **8.2 SAFETY AND OTHER ASSESSMENTS**

Vitamin D is a very safe supplement with a large therapeutic index. Vitamin D sufficiency is considered to be greater than 30 ng/ml. Intoxication does not occur until serum 25(OH)D levels exceed 150 ng/ml (325 nmol/L).(85) However, most clinical laboratories consider 100 ng/ml to be the upper limit in order to maintain a wide safety margin. Reports of vitamin D toxicity are rare and virtually always related to faulty manufacturing or labeling of product such that individuals ingested hundreds to thousands of times the presumed dose.(86, 87) The consequence of vitamin D toxicity is hypercalcemia. Hypercalcemia only results when 25(OH)D concentrations have consistently been above 150-200 ng/ml (375-500 nmol/L).(85)

To ensure safety in this study, spot urine calcium/creatinine levels will be measured at each visit as a screen for hypercalciuria. The study coordinator will instruct the participant and his or her parent, legal guardian, or caregiver to ensure that the child is well-hydrated prior to the study visit. If the urine calcium/creatinine level is greater than 0.37 on a specimen, the participant will be asked again to ensure good hydration and return within 2 business days for a repeat spot urine calcium/creatinine measurement. If the ratio remains greater than 0.37, then a serum calcium level and 25(OH)D for the local laboratory will be obtained.(75) If serum calcium is greater than  $1.5 \times \text{ULN}$  or the 25(OH)D level is greater than 100 ng/ml, the participant will have supplementation stopped but will be asked to return for remaining study visits in order to obtain data on vitamin D clearance and for safety assessments. Vitamin D supplementation ends at 16 weeks (day  $112 \pm 7$ ) for all participants. They will be followed for another twelve weeks for determination of elimination kinetics and for safety assessments. The half-life of vitamin D is variable but is felt to be approximately 2 months.(88) The 12-week follow-up therefore consists of 1.5 half-lives. A serum 25(OH)D level will be drawn for the local laboratory safety measure at week 28 (visit 9; day  $196 \pm 7$ ). If a participant has a serum 25(OH)D level greater than 80 ng/ml at that time, he/she will be asked to return 4 weeks later for a re-check to ensure that the level is not continuing to rise as vitamin D washes out of adipose tissue. If there are any ongoing concerns, further follow up will be determined by the local investigator in collaboration with the child's primary care team and sub-specialists as necessary.

This is not an asthma treatment study. We will monitor asthma symptoms, however. Each participant is required to have an identified asthma-care provider at entry. This can be a specialist or a primary care provider. If it is found that a participant's asthma is poorly controlled, he or she will be referred back to the primary asthma-care provider for reevaluation and further treatment.

If any child is found to be in the midst of an asthma exacerbation at the time of a study visit, the study staff will notify the local PI and take appropriate action to guarantee safety of the child. This may include referral to an Urgent Care or Emergency facility or may involve the local PI treating the participant if he or she is the child's asthma care provider.

## 8.3 ADVERSE EVENTS AND SERIOUS ADVERSE EVENTS AND ADVERSE REACTIONS

### 8.3.1 DEFINITION OF ADVERSE EVENTS AND ADVERSE REACTIONS

AE means any untoward medical occurrence associated with the use of an intervention in humans, whether or not considered intervention related.

AR means any adverse event caused by a drug. Adverse reactions are a subset of all suspected adverse events where there is reason conclude that the drug caused the event.

### 8.3.2 DEFINITION OF SERIOUS ADVERSE EVENTS OR REACTIONS

An AE or suspected AR is considered "serious" if, in the view of either the investigator or sponsor, it results in any of the following outcomes:

- death
- a life-threatening adverse event
- inpatient hospitalization or prolongation of existing hospitalization
- a persistent or significant incapacity or substantial disruption of the ability to conduct normal life functions
- a congenital anomaly/birth defect
- important medical events that may not result in death, be life-threatening, or require hospitalization may be considered serious when, based upon appropriate medical judgment, they may jeopardize the participant and may require medical or surgical intervention to prevent one of the outcomes listed in this definition. Examples of such medical events include allergic bronchospasm requiring intensive treatment in an emergency room or at home, blood dyscrasias or convulsions that do not result in inpatient hospitalization, or the development of drug dependency or drug abuse.

### 8.3.3 CLASSIFICATION OF AN ADVERSE EVENT

#### 8.3.3.1 SEVERITY OF EVENT

For AEs and ARs not included in the protocol-defined grading system, the following guidelines will be used to describe severity. The site investigator will determine severity.

- **Mild** – Events require minimal or no treatment and do not interfere with the participant's daily activities.
- **Moderate** – Events result in a low level of inconvenience or concern with the therapeutic measures. Moderate events may cause some interference with functioning.
- **Severe** – Events interrupt a participant's usual daily activity and may require systemic drug therapy or other treatment. Severe events are usually potentially life-threatening or incapacitating. Of note, the term "severe" does not necessarily equate to "serious."

#### 8.3.3.2 RELATIONSHIP TO STUDY INTERVENTION

All AEs must have their relationship to study intervention assessed by the clinician who examines and evaluates the participant based on temporal relationship and his/her clinical judgment. The degree of certainty about causality will be graded using the categories below. In a clinical trial, the study product must always be suspect.

- **Definitely Related** – There is clear evidence to suggest a causal relationship, and other possible contributing factors can be ruled out. The clinical event, including an abnormal laboratory test result, occurs in a plausible time relationship to study intervention administration and cannot be explained by concurrent disease or other drugs or chemicals. The response to withdrawal of the study intervention (dechallenge) should be clinically plausible. The event must be pharmacologically or phenomenologically definitive, with use of a satisfactory rechallenge procedure if necessary.
- **Probably Related** – There is evidence to suggest a causal relationship, and the influence of other factors is unlikely. The clinical event, including an abnormal laboratory test result, occurs within a reasonable time after administration of the study intervention, is unlikely to be attributed to concurrent disease or other drugs or chemicals, and follows a clinically reasonable response on withdrawal (dechallenge). Rechallenge information is not required to fulfill this definition.

- **Potentially Related** – There is some evidence to suggest a causal relationship (e.g., the event occurred within a reasonable time after administration of the trial medication). However, other factors may have contributed to the event (e.g., the participant's clinical condition, other concomitant events). Although an AE may rate only as "possibly related" soon after discovery, it can be flagged as requiring more information and later be upgraded to "probably related" or "definitely related," as appropriate.
- **Unlikely to be related** – A clinical event, including an abnormal laboratory test result, whose temporal relationship to study intervention administration makes a causal relationship improbable (e.g., the event did not occur within a reasonable time after administration of the study intervention) and in which other drugs or chemicals or underlying disease provides plausible explanations (e.g., the participant's clinical condition, other concomitant treatments).
- **Not Related** – The AE is completely independent of study intervention administration, and/or evidence exists that the event is definitely related to another etiology. There must be an alternative, definitive etiology documented by the clinician.

#### 8.3.3.3 EXPECTEDNESS

The expectedness of an AE or suspected AR shall be determined according to the specified reference document containing safety information (e.g., most current product information or product label). Any AE that is not identified in nature, severity, or specificity in the current study drug reference document(s) (e.g., product information) is considered unexpected. Events that are mentioned in the product information as occurring with a class of drugs or as anticipated from the pharmacological properties of the drug, but not specifically mentioned as occurring with the particular drug in this study are considered unexpected.

Expected AEs that could occur in this study are: bruising related to venipuncture/fingerstick, pain related to venipuncture/fingerstick, increase in calcium in the blood or urine, kidney stones, accidental vitamin D poisoning (associated nausea and increased levels of calcium in the blood), increased urination, decreased appetite, increased fatigue, hypersensitivity to vitamin D, or hypercalcemia (only expected when vitamin D blood level is above 150-200 ng/mL, but the intervention will be stopped if level reaches 100 ng/mL).

If the capsule is ruptured or broken, the powder may cause the following: irritation or burning of the eyes, skin, or respiratory system (if inhaled).

#### 8.3.4 TIME PERIOD AND FREQUENCY FOR EVENT ASSESSMENT AND FOLLOW-UP

The occurrence of an AE or SAE may come to the attention of study personnel during study visits and interviews of a study participant presenting for medical care, or upon review by a study monitor. All AEs including local and systemic reactions will be captured on the appropriate CRF. Information to be collected includes event description, time of onset, clinician's assessment of severity, relationship to study product (assessed only by those with the training and authority to make a diagnosis), and time of resolution/stabilization of the event. All AEs occurring while on study must be documented appropriately regardless of relationship. All AEs must be followed until 1 of the following criteria is met: resolution, the condition stabilizes, the event is otherwise explained or is judged by the PI to be no longer clinically significant, or the participant is lost to follow-up.

Any medical condition that is present at the time that the participant is screened will be considered as baseline and not reported as an AE. However, if the study participant's condition deteriorates at any time during the study, it will be recorded as an AE. Changes in the severity of an AE will be documented to allow an assessment of the duration of the event at each level of severity to be performed. AEs characterized as intermittent require documentation of onset and duration of each episode. At each study visit, the investigator or study coordinator will inquire about the occurrence of AE/SAEs since the last visit. The site investigator will record all reportable events with start dates occurring any time after informed consent is obtained. Events will be followed for outcome information until resolution or stabilization or until 7 days (for non-serious AEs) or 30 days (for SAEs) after the last day of study participation.

#### 8.3.5 ADVERSE EVENT AND REACTION REPORTING

All AEs and ARs that occur after informed consent is obtained until 7 days after the last day of study participation should be documented in the patient's source documents in accordance with the Investigator's normal clinical practice and in the AE section of the CRF.

#### 8.3.6 SERIOUS ADVERSE EVENT AND REACTION REPORTING

The site investigator will report all SAEs and SARs occurring any time after informed consent is obtained until 30 days after the last day of study participation. The study clinician will immediately report to the sponsor any SAE, whether or not considered study intervention related, including those listed in the protocol or product information and must include an assessment of whether there is a reasonable possibility that the study intervention caused the event. Study endpoints that are SAEs (e.g., all-cause mortality) must be reported in accordance with the protocol unless there is evidence suggesting a causal relationship between the study intervention and the event (e.g., death from anaphylaxis). In that case, the investigator must immediately report the event to the sponsor.

The investigator/qualified designee will enter the required information regarding the SAE into the appropriate module of the electronic case report form (eCRF), which will automatically result in distribution of the information to the appropriate sponsor contact. If the eCRF system is temporarily unavailable, the event, including the investigator-determined causality to study drug, must be reported via a paper back-up SAE form to the appropriate sponsor contact. Upon return of the availability of electronic data capture system, the SAE information must be entered into the eCRF.

All SAEs will be followed until resolution or until the site investigator deems the event to be chronic, or until the participant is stable, or until 30 days after the last day of study participation. Other supporting documentation of the event may be requested by the DCOC/study sponsor and should be provided as soon as possible.

#### 8.3.7 REPORTING EVENTS TO PARTICIPANTS

The participants will be notified of those study-related (or potentially study-related) SAEs, SARs and unanticipated problems (UPs) that may affect either the participants' willingness to continue with the study or the future health of the child enrolled in the study. This determination can be made by any of the following: the IRB, the medical monitor, the DSMB, or the sponsor. The person or oversight body that makes the determination will inform the DCOC, which will instruct the site PIs/study coordinators to contact those participants enrolled through their site. Contacts with participants, if necessary, will be recorded on the appropriate CRF and/or study log.

#### 8.3.8 EVENTS OF SPECIAL INTEREST

Not applicable.

#### 8.3.9 REPORTING OF PREGNANCY

As noted above in Section 2.3.1, vitamin D supplementation is safe in pregnancy. However, to be extremely cautious, participants of childbearing potential will be counseled to use acceptable forms of birth control as well as condoms during the study period. Abstinence is considered an acceptable form of birth control. There are no known risks of vitamin D intake during pregnancy.

We will follow standard pharmaceutical study practices in regards to pregnancy to make sure we account for the possibility of untoward and unexpected effects on a fetus. If a participant becomes pregnant during the study, dosing will be discontinued immediately.

If a subject reports a pregnancy, we will use a specific pregnancy follow-up form to track the outcome of the pregnancy for the subject. On this form, we will document how the pregnancy diagnosis was made, whether the subject has received a medical evaluation for the pregnancy (and where), and what the outcome of the pregnancy was (e.g., miscarriage, elective abortion, live birth or stillbirth). We will also record maternal history (including congenital abnormalities or pregnancy complications) and estimated date of conception.

The pregnant participant will be followed until delivery or until the end of pregnancy (in the case of miscarriage or pregnancy termination). This will occasionally require us to follow participants after they have completed this study.

For all live births, we will document the mode of delivery, gestational delivery age, the birth weight, whether there were any health problems (infant and/or mother) at delivery, and whether the baby required a hospitalization beyond 2 days. These data will all be self-reported by the participant. We will monitor all pregnancy-related outcomes, and will request permission to obtain medical records for any participant in which adverse pregnancy-related outcomes are reported.

Any associated AEs or SAEs that occur to the mother or fetus/child will be recorded in the AE or SAE eCRF.

## 8.4 UNANTICIPATED PROBLEMS

### 8.4.1 DEFINITION OF UNANTICIPATED PROBLEMS

The Office for Human Research Protections (OHRP) considers unanticipated problems involving risks to participants or others to include, in general, any incident, experience, or outcome that meets all of the following criteria:

- Unexpected in terms of nature, severity, or frequency given (a) the research procedures that are described in the protocol-related documents, such as the IRB-approved research protocol and informed consent document; and (b) the characteristics of the participant population being studied;
- Related or possibly related to participation in the research (“possibly related” means there is a reasonable possibility that the incident, experience, or outcome may have been caused by the procedures involved in the research); and
- Suggests that the research places participants or others at a greater risk of harm (including physical, psychological, economic, or social harm) than was previously known or recognized.

An unanticipated problem is not necessarily an AE or SAE. Unanticipated problems that are neither an AE nor SAE, but which must be reported, are listed below in Section 8.4.2.

### 8.4.2 UNANTICIPATED PROBLEM REPORTING

Unanticipated problems (per Section 8.4.1) must be reported to the reviewing IRB, the DCOC, the sponsor, and the NIH DSMB as well as any other persons or groups noted in the DSMB charter. These problems must be reported to the reviewing IRB according to the reviewing IRB’s policies and procedures and reported to local institutions according to the rules and regulations of the local institution. The reviewing IRB will report the issue to OHRP per the policies of the reviewing IRB. For the UAMS IRB, which will be the reviewing IRB for most of the sites for this study, the required reporting times are shown in the following table.

**Table 3. Unanticipated Problem Reporting**

Unanticipated Problem	Required Reporting Time to UAMS IRB
Death or life-threatening	Immediately to IRB office or IRB Chair
All other events	Within 10 days of event or notification of event if non-local

Examples of unanticipated problems that are not an AE or SAE, but which would need to be reported include:

- Breach of confidentiality
- Change in product labeling, or withdrawal from marketing, of the vitamin D used in this protocol

Typically, the report to the IRB et al. will include the following:

- Protocol identification information (title, number, etc.)
- PI name
- Detailed description of event
- Explanation of why the event is a UP
- Description of changes needed (to protocol) and/or other corrective actions taken or needed

Additional details are provided in the study-specific MOP.

#### **8.4.3 REPORTING UNANTICIPATED PROBLEMS TO PARTICIPANTS**

The participants will be notified only of those study-related (or potentially study-related) SAEs and unanticipated problems that may affect either the participants' willingness to continue with the study or the future health of the participant enrolled in the study. This determination can be made by any of the following: the IRB, the medical monitor, the DSMB, or the sponsor. The person or oversight body that makes the determination will inform the DCOC, which will instruct the site PIs/study coordinators to contact those participants enrolled through their site.

Contacts with participants, if necessary, will be recorded on the appropriate CRF and/or study log.

## 9 STATISTICAL CONSIDERATIONS

### 9.1 STATISTICAL HYPOTHESES

Study objective: The overall objective of this study is to determine the PK of Vitamin D supplementation in children who have asthma and are overweight or obese and therefore no formal hypothesis testing will be performed.

Part 1 Objective: Identify dosing to use in Part 2 using PK analysis on a subset of participants  
Part 2 Objective: Determine the effectiveness of a recommended 16-week dosing regimen to achieve a serum level of 25(OH)D greater than or equal to 40 ng/ml in vitamin D insufficient or deficient children who have asthma and are overweight/obese

The hypothesis for Part 2 will be tested using the one-group Chi-square test at the 5% one-sided significance level.

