### 9.2 SAMPLE SIZE DETERMINATION

Part 1: a sample size of greater than 50 participants will be powered (greater than 80%) to target a 95% confidence interval within 60% and 140% of the geometric mean estimates of 25(OH)D systemic clearance. The sample size assumes a coefficient of variation of 50% in 25(OH)D steady-state concentration.(48, 89) Based on prior experience (90, 91, 92, 93) a sample size of 16 participants in the interim analysis will suffice to determine a recommended dose for Part 2.

Part 2: For the optimal dosing regimen defined by the interim PK-analysis, the null hypothesis that the proportion of children who achieve a vitamin D level of greater than or equal to 40 ng/ml is 50% or less at 16 weeks will be tested against the alternative hypothesis that the proportion is 75% or more at the one-sided 0.05 significance level with power of 0.90. Using the one group Chi-square test for testing a single proportion, the number of study participants required to complete Part 2 is 31 participants. To allow for an approximately 30% dropout rate (due, in part, to the COVID-19 pandemic), 63 participants will be randomized to (A) the 8,000 IU daily dose (with a 50,000 IU loading dose) regimen or to (B) the standard of care (600 IU/day) dose. The allocation ratio will be 2:1 (A:B).

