#### 9.4.4 ANALYSIS OF PART 2 ENDPOINTS

The participants who achieve a vitamin D level of greater than or equal to 40 ng/ml will be estimated along with the corresponding 95% confidence interval for each dose regimen in Part 1. A one-group test of proportion will be used to analyze the overall proportion of participants with 25(OH)D greater than or equal to 40 ng/ml at 16 weeks among participants treated with the final recommended dose in Part 2.

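### The Part 2 chi-square test is a large-sample approximation applied to a small binomial count: 31 completers give exact power 0.87, not 0.90, and the 5% level holds at a Cohort A size of 42 but not at 41 or 43.

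*Combined protocol and SAP*

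**What the plan says.** Section 9.1 names the test and its level: "The hypothesis for Part 2 will be tested using the one-group Chi-square test at the 5% one-sided significance level".

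Section 9.2 gives the hypotheses. The null puts the 16-week rate of reaching 40 ng/ml no higher than one half. The alternative, with the level and power, reads: "that the proportion is 75% or more at the one-sided 0.05 significance level with power of 0.90". On the sample size, the section states: "Using the one group Chi-square test for testing a single proportion, the number of study participants required to complete Part 2 is 31 participants". The number randomised is raised to 63, split 2:1, "To allow for an approximately 30% dropout rate". An exact 2:1 split puts 42 children in Cohort A.

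Section 9.4.4 is less specific: "A one-group test of proportion will be used to analyze the overall proportion of participants with 25(OH)D greater than or equal to 40 ng/ml". Section 9.4.3 repeats this. Neither section names an exact or continuity-corrected version.

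Two other sections fix the denominator. Section 9.3 uses the intent-to-treat population for all non-PK analyses, and section 9.5 scores premature withdrawals as non-responders in the primary analysis. Section 6.3 stratifies the block randomisation by two age groups and three BMI groups, without giving a block size.

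**The concern.** The responder count in Cohort A is binomial with a few dozen trials. An uncorrected chi-square test on such a count rejects at a whole number of responders, so its true one-sided error rate moves up and down with n instead of staying at 5%. Power calculated from the normal curve has the same weakness.

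This is the only test in the plan with a stated null, level and power, and it is the formal test of the Part 2 objective. Two things are at stake. Section 9.2 states a power that its own sample size does not deliver, even if all 31 children are measured. And whether the 5% level holds depends on whether Cohort A ends with 41, 42 or 43 children.

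**Working it through.** **Inputs.** Null 0.50, alternative 0.75, one-sided level 0.05, power 0.90 and 31 completers (section 9.2); 63 randomised 2:1 (9.2); about 30% dropout (9.2); one-group chi-square test (9.1, 9.2).

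**1. Reproduce the plan's figure.** The one-sample normal formula is

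n = [(z₀.₉₅·√(p₀q₀) + z₀.₉₀·√(p₁q₁)) / (p₁ − p₀)]²

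= [(1.645 × 0.5 + 1.2816 × √0.1875) / 0.25]² = 30.35, rounded up to 31. Approximate power at 31 is 0.906. The stated number follows from the method named.

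**2. Exact behaviour.** The chi-square test rejects at the smallest r with (r − n/2)/√(n/4) ≥ 1.645. Its exact size is P(Bin(n, 0.50) ≥ r) and its exact power is P(Bin(n, 0.75) ≥ r). The exact binomial test uses the smallest r whose size is at most 0.05.

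At n = 31, r = 20 gives z = (20 − 15.5)/2.784 = 1.616, which is too small. r = 21 gives 1.976, so 21 responders are needed. Exact size is 0.0354 and exact power 0.8716.

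| n | Chi-square r | size | power | Exact r | size | power |
|---|---|---|---|---|---|---|
| 29 | 19 | 0.068 | 0.915 | 20 | 0.031 | 0.834 |
| 31 | 21 | 0.035 | 0.872 | 21 | 0.035 | 0.872 |
| 33 | 22 | 0.040 | 0.901 | 22 | 0.040 | 0.901 |
| 34 | 22 | 0.061 | 0.939 | 23 | 0.029 | 0.881 |
| 35 | 23 | 0.045 | 0.924 | 23 | 0.045 | 0.924 |
| 41 | 26 | 0.059 | 0.967 | 27 | 0.030 | 0.933 |
| 42 | 27 | 0.044 | 0.958 | 27 | 0.044 | 0.958 |
| 43 | 27 | 0.063 | 0.975 | 28 | 0.033 | 0.949 |

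Under the exact test, power first reaches 0.90 at 33, falls back at 34, and is at or above 0.90 at every n from 35 to 63.

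**3. Which n applies.** I read sections 9.3 and 9.5 together as making the primary denominator all children randomised to Cohort A. At 63 × 2/3 = 42 the level holds. But 63 children spread over 2 × 3 = 6 strata leave incomplete blocks, so 42 is not guaranteed. The block size and stratum mix are not given. Assuming blocks of 3 or 6 and six equally likely strata, 20,000 simulated allocations of 63 children for each block size gave:

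- Cohort A is exactly 42 in about 42% (blocks of 3) or 31% (blocks of 6) of allocations.
- The size is one where the chi-square test exceeds 5%, mainly 41 or 43, in about 49% of allocations with either block size.
- The true size averaged over allocations is 0.0523 (blocks of 3) or 0.0520 (blocks of 6).

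**4. Completers analysis.** 42 × 0.70 = 29.4, so about 29 children. The chi-square test then has true size 6.8%. This is not the primary denominator.

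**The case against.** The strongest reply is that little changes in practice. At 31 and at 42, the two sizes that the plan itself implies, the chi-square and exact tests reject at the same count and the level holds. Averaged over plausible allocations, the excess over 5% is about 0.2 percentage points. The shortfall at 31 is 2.8 points (0.900 − 0.872), and 42 evaluable children would give 0.958. All of this stands, and it keeps the point modest.

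It can also be said that section 9.4.1 leaves detail to a separate SAP and that section 9.4.4 does not exclude an exact or continuity-corrected test; the corrected version holds 5% at every n from 25 to 63. This is only a partial answer, because sections 9.1 and 9.2 name the chi-square test, the level, the power and the 31 without qualification.

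Four stronger readings are tempting, and the documents do not support them:

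- **That this is the only hypothesis test in the trial.** Section 9.5 plans a chi-square or Fisher comparison with standard of care, and section 9.4.10 plans estimating-equation models.
- **That 31 is an arithmetic error.** It follows from the approximation the protocol names; the gap is between approximate and exact power.
- **That the primary analysis runs at 6.8%.** That figure belongs to 29 completers, whereas the primary analysis keeps withdrawals in the denominator.
- **That the dose is confirmed or rejected on this p-value alone.** No section gives such a decision rule.

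**Conclusion.** The point holds in a limited form. Exact power at the stated 31 completers is 0.87, whatever is assumed about dropout, provided that all 31 are measured and the true rate is 75%. In the primary analysis the named test holds 5% at exactly 42 but runs at 5.9% with 41 and 6.3% with 43. The 49% frequency and the 5.2% average rest on the assumed block sizes and equal strata, and on randomising all 63. Recruitment of fewer children, which the wording of section 4.1 allows, would move the denominator to other sizes, some of which also exceed 5%.

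The loss of power from scoring withdrawals as non-responders is a separate matter. It is neither counted here nor cured by changing the test.

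**What to change.** In sections 9.1, 9.2, 9.4.3 and 9.4.4, name the exact one-sided binomial test of 50% at the 0.05 level, with the critical count read from the realised Cohort A size: 27 of 41, 27 of 42 or 28 of 43. In section 9.2, state that 31 evaluable children give exact power 0.87 against 75%, and that 35 or more give at least 0.90.

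The cost is protocol and SAP wording only. No sample size changes, and no decision changes at 31 or 42. Power falls somewhat where the chi-square test was liberal: from 0.97 to 0.93 at 41, and from 0.91 to 0.83 at 29.
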